5.3. Dosage and Administration of GS-9131, BIC, DRV, RTV, TAF and PTM GS-9131

Study drug GS-9131, BIC, DRV, RTV, TAF, and PTM GS-9131 tablets will be provided by Gilead.

In Sentinel Cohort 1, subjects will begin assigned GS-9131 60 mg once daily. All other ARVs in the current regimen will be continued. All ARVs, including GS-9131, will be administered by directly observed therapy (DOT) on Days 1-10. If the current regimen includes ARVs taken more than once daily, taken at night, or with certain meals, additional doses will be documented

by the subject in a dosing diary provided for the study. GS-9131 must be administered by DOT on Days 1-10. Subjects who successfully complete all study drug doses through Day 10 and show a reduction in plasma HIV RNA $> 0.5 \log_{10}$ from their pre-GS-9131 baseline during functional monotherapy will discontinue their current failing regimen, and start an optimized regimen consisting of GS-9131 (60 mg) + BIC (30 mg) + DRV (800 mg) + RTV (100 mg) for 24 Weeks.

In Sentinel Cohort 2 and the Randomized Cohort, Part 1, subjects will begin assigned GS-9131 doses up to 180 mg, or PTM once daily. All other ARVs in the current regimen will be continued. All ARVs, including GS-9131, will be administered by directly observed therapy (DOT) on Days 1-14. If the current regimen includes ARVs taken more than once daily, taken at night, or with certain meals, additional doses will be documented by the subject in a dosing diary provided for the study. GS-9131 must be administered by DOT on Days 1-14.

Subjects in Sentinel Cohort 2 and Randomized Cohort Treatment Arms A-C who successfully complete all study drug doses in Part 1 and show a reduction in plasma HIV RNA $> 0.5 \log_{10}$ from their pre-GS-9131 baseline during functional monotherapy will enroll in Part 2, discontinue their current failing regimen, and start an optimized regimen consisting of GS-9131 (up to 180 mg) + BIC (75 mg) + TAF (25 mg). The GS-9131 dose in the combination regimen will be defined by the open-label or randomization dose given in Part 1. Reduction of plasma HIV RNA $> 0.5 \log_{10}$ from baseline must be demonstrated at Day 15. Dose of GS-9131 for the Randomized Cohort will be determined following review of Sentinel Cohort 2. The dose of GS-9131 for the OLE will be determined following review of the safety, efficacy and available PK data of the Randomized Cohort in Part 1 from Part 2.

CCI

Subjects will be instructed to bring all study medication in the original container to each clinic visit for drug accountability (unless otherwise specified in Section 5.5). The Investigator will be responsible for maintaining accurate records for all study drug bottles dispensed and tablets returned. The inventory and dispensing logs must be available for inspection by the study monitor. Study medication supplies, including partially used or empty bottles, must be accounted for by the study monitor prior to destruction or return.

5.4. Prior and Concomitant Medications For Subjects in Sentinel Cohort 2, Randomized Cohort and Part 2: GS-9131 + BIC + TAF

Invitro data suggest GS-9131 is a substrate of Pgp transporters and an inhibitor of OATP1B/1B3 transporters. Concomitant use of some medications and herbal/natural supplements with study drug may result in pharmacokinetic interactions resulting in increases or decreases in exposure of study drugs or these medications.

Representative medications listed in the following table and herbal/natural supplements are excluded or should be used with caution while subjects are participating in the study, this table is not exhaustive. During Part 1 of the study, physicians should also refer to the prescribing information for the current background regimen in addition to the recommendations listed in the table below. Subjects should discontinue disallowed concomitant medications 30 days prior to initiation of study drug.

In Part 2, the use of medications for the treatment of HIV, other than GS-9131 + BIC + TAF, are prohibited.

Table 6. Prior and Concomitant Medications*

Drug Class	Agents Disallowed**	Use Discouraged and To Be Used With Caution
Medications or oral supplements containing polyvalent cations (e.g., Mg, Al, Ca, Fe): Calcium or iron supplements Cation-containing antacids or laxatives Buffered medications		Administer Study Drug 2 hours before or 2 hours after taking medications or oral supplements containing polyvalent cations. Alternatively, Study Drug and medications or oral supplements containing polyvalent cations can be taken together with food.
Antiarrhythmic Agent	Dofetilide	
Anticonvulsants	Phenobarbital, Phenytoin, Carbamazepine, Oxcarbazepine	
Antimycobacterials	Rifampin, Rifapentine, Rifabutin	
Antiretrovirals	Any antiretroviral drug that is not part of the study regimen	
Statins		Pravastatin, pitavastatin, rosuvastatin, atorvastatin: Monitor for statin-related AEs
Herbal/Natural Supplements	St. John's Wort	

* For Prior and Concomitant Medications relevant to subjects in Part 2: DRV/r+BIC+GS-9131, see [Appendix 8](#).

** Administration of any of the above medications must be discontinued at least 30 days prior to the Day 1 visit and for the duration of the study

Should subjects have a need to initiate treatment with any excluded concomitant medication, the Gilead Medical Monitor must be consulted prior to initiation of the new medication. In instances where an excluded medication is initiated prior to discussion with the Sponsor, the Investigator must notify Gilead as soon as he/she is aware of the use of the excluded medication.

5.5. Accountability of IMP

The investigator is responsible for ensuring adequate accountability of all used and unused IMP. This includes acknowledgement of receipt of each shipment of IMP (quantity and condition). All used and unused IMP dispensed to subjects must be returned to the site.

Study drug accountability records will be provided to each study site to:

- Record the date received and quantity of IMP kits
- Record the date, subject number, subject initials, and the IMP kit number dispensed
- Record the date, quantity of used and unused IMP kits returned, along with the initials of the person recording the information.

5.6. Investigational Medicinal Product Return or Disposal

Study drug return and disposal will be performed as outlined in Section [9.1.7](#).

6. STUDY PROCEDURES

The study procedures to be conducted for each subject enrolled in the study are presented in tabular form in [Appendix 2](#) and [Appendix 3](#) and described in the text that follows.

The investigator must document any deviation from protocol procedures and notify the sponsor or contact research organization (CRO).

6.1. Subject Enrollment and Treatment Assignment

It is the responsibility of the Investigator to ensure that subjects are eligible for the study prior to enrollment.

6.2. Pretreatment Assessments

6.2.1. Screening Visit

Subjects will be screened within 30 days before Part 1 Day 1 to determine eligibility for participation in the study. A single 14 day extension to the screening window may be granted with permission from the Medical Monitor. The following will be performed and documented at screening:

- Obtain written informed consent
- Obtain medical history, including history of HIV-1 disease-related events, complete ARV treatment history and all prior medications within 30 days of the Screening visit
- Complete physical examination (urogenital/anorectal exams will be performed at the discretion of the Investigator)
- Height
- Vital signs measurement (blood pressure, pulse, respiration rate, and temperature), including weight
- 12-lead ECG performed supine
- Obtain blood and urine samples as described in Sections [6.8.1](#), [6.8.2](#), [Appendix 2](#), and [Appendix 3](#).
- Review and document locally performed HIV resistance data including genotype and/or phenotype
 - HIV-1 genotype testing (integrase, protease, and reverse transcriptase) can be performed locally or centrally at the screening visit. Central lab HIV-1 genotype testing will not be performed for subjects that fail to meet other eligibility criteria.
- Review of AEs and concomitant medications

Subjects that meet all of the inclusion criteria and none of the exclusion criteria will return to the clinic within 30 days after screening for the Day 1 Visit. Subjects must continue to take their prior treatment regimen until they are instructed to do otherwise. Subjects will be required to take their prior regimen through completion of Part 1 until the initiation of the Part 2 regimen.

From the time of obtaining informed consent through the first administration of IMP, all serious adverse events (SAEs), as well as any AEs related to protocol-mandated procedures, will be recorded on the AE eCRF. All other untoward medical occurrences observed during the screening period, including exacerbation or changes in medical history, will be captured on the medical history eCRF. See Section 7 Adverse Events and Toxicity Management for additional details.

6.3. Treatment Assessments

6.3.1. Part 1 – Functional Monotherapy (Sentinel and Randomized Cohorts)

Subjects who meet criteria will first be enrolled in the Sentinel Cohort 1. The Sentinel Cohort 1 is an open-label cohort that will enroll approximately 10 HIV-1 positive subjects to receive GS-9131 60 mg plus their current failing regimen for 10 days. The Sentinel Cohort 2 is an open-label cohort that will enroll approximately 10 HIV-1 positive subjects to receive GS-9131 180 mg plus their current failing regimen for 14 days.

Randomization and dosing into the Randomized Cohort of Part 1 will begin after review of the Day 15 safety and efficacy, and available PK data from the Sentinel Cohort 2.

Once eligibility has been confirmed for the Randomized Cohort and prior to or during the Part 1 Day 1 visit, the Investigator or designee will randomize the subject using the Interactive Web Response System (IWRS). Once a subject number has been assigned to a subject, it will not be reassigned to any other subject. The subject number assignment and randomization may be performed up to 3 days prior to the in-clinic Part 1 Day 1 visit provided that all screening procedures have been completed and subject eligibility has been confirmed. The Investigator must have results from genotype testing and confirm eligibility before proceeding with randomization.

- Review concomitant medications
- Record any SAEs and all AEs related to protocol mandated procedures occurring after signing of the consent form.
- Complete physical examination (urogenital/anorectal exams will be performed at the discretion of the Investigator) (**Screening, Day 1, 14, and 15**)
- Symptom-directed physical examination (**Days 2, 7, 10, and 14**)
- Vital signs measurement (blood pressure, pulse, respiration rate, and temperature), including weight (**Screening, Days 1, 3, 7, 10, and 14**)

- 12-lead ECG performed supine (approximately 1 hour post dose) (**Screening, Days 1, 10, and 15**)
- Obtain blood and urine samples as described in Sections [6.8.1](#), [6.8.2](#), [Appendix 2](#), and [Appendix 3](#).
- Collect subject dosing diary from all subjects (**Day 15**)
- Administration of study drug by DOT. Study drug, as well as other ARVs, will be administered by DOT once daily. Any additional doses of ARVs, other than GS-9131, that cannot be administered at the same time will be documented by the subject in a dosing diary provided for the study. Study drug should be administered at approximately the same time each day.

6.3.2. Part 2

All subjects must complete Part 1 prior to initiating any Part 2 Day 1 Visit procedures. Before proceeding into Part 2, subjects who have completed Day 14 of Part 1 will discontinue GS-9131 or PTM but remain on their failing regimen until the site is notified of the subject's eligibility to proceed to Part 2. This period shall be no longer than 14 days (for Sentinel Cohort 1)/9 days (Sentinel Cohort 2 and Randomized Cohort), while awaiting HIV-1 RNA results and the authorization to proceed from Gilead.

Once notified of their eligibility into Part 2 of the study, the subject will discontinue their failing regimen before initiating any Part 2 Day 1 study procedures. Subjects who received GS-9131 (including all subjects in the Sentinel Cohort 2 and those on Treatment Arms A-C of the Randomized Cohort) and had a $\leq 0.5 \log_{10}$ decline in HIV-1 RNA will be discontinued from the study early and will have a 30 day visit following this visit.

In the event the plasma HIV-1 RNA test results performed by the central laboratory are delayed, a subject may still proceed to Part 2 of the study if the test results from the local laboratory show a reduction in plasma HIV-1 RNA $> 0.5 \log_{10}$ compared to pre-GS-9131 baseline during the 14 days of GS-9131 functional monotherapy in Part 1 of the study. If the local laboratory test results do not show a reduction in plasma HIV-1 RNA $> 0.5 \log_{10}$ and the central laboratory test results are not received ≤ 9 days from completion of Day 15 of Part 1, the subject will be discontinued from the study and will be required to return to the clinic 30 days after the last dose of study drug for the 30-Day Follow-Up Visit. After a subject has terminated their participation in the study, long-term care for the subject will remain the responsibility of their primary treating physician, who will have access to the subject's clinical information, including plasma HIV-1 RNA viral load and HIV-1 genotype testing results.

Part 2 Day 1 Treatment Assessments

All subjects who successfully complete all study drug doses in Part 1 and meet criteria to proceed to Part 2 will transition to Part 2 and discontinue their current failing regimen.

The following evaluations are to be completed on Day 1 of Part 2. The Investigator must have confirmed eligibility before proceeding with the Part 2 Day 1 visit. The subject must complete all study procedures before being administered the study drug. Initiation of treatment with the study drug must take place within 24 hours after the Day 1 visit.

- Review concomitant medications
- Record any SAEs and all AEs related to protocol mandated procedures occurring after signing of the consent form
- Complete physical examination (urogenital/anorectal exams will be performed at the discretion of the Investigator)
- Vital signs measurement (blood pressure, pulse, respiration rate, and temperature), including weight
- Obtain blood and urine samples as described in Sections [6.8.1](#), [6.8.2](#), [Appendix 2](#), and [Appendix 3](#)
- Document study drug dispensation and accountability for all study drugs dispensed
 - Subjects must be reminded to take study drug at the same time each day with food

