Laboratory analyses (hematology, chemistry, and urinalysis) will be performed at Day 1 (baseline), Day 7, and Day 11. A fasting metabolic profile will be performed on Day 1. Urine and serum pregnancy test (females of childbearing potential only) will be done at Screening and Day 1 and a urine pregnancy test on Day 11; positive urine pregnancy test on Day 11 will be confirmed with a serum pregnancy test. CD4 T cell count will be performed at Screening, Day 1 (baseline), and Day 11. A plasma sample for phenotypic and genotypic testing of HIV-1 resistance will be collected at Screening, Day 1, and Day 11. A complete physical examination will be performed at Screening, Day 1 (baseline), and Day 11. Symptom driven physical exam will be performed on Day 2 and Day 7. ECGs will be performed at Screening, Day 1, and Day 11.

On Day 10, all subjects will participate in a PK evaluation.

Samples for HIV-1 RNA will be collected at Screening, Day 1 (baseline), and Days 2, 3, 7, 10, and 11.

Assessments of AEs and concomitant medications will be performed at each visit.

Sentinel Cohort 2 (GS-9131 180 mg plus Current Failing Regimen) and Randomized Cohort (GS-9131 or PTM plus Current Failing Regimen)

Following Screening and Day 1 (baseline) visits, all study medication will be delivered by DOT on Days 1-14.

Laboratory analyses (hematology, chemistry, and urinalysis) will be performed at Days 1 (baseline), 3, 5, 7, 10, 14, and 15. A fasting metabolic profile will be performed on Day 1. Urine and serum

pregnancy test (females of childbearing potential only) will be done at Screening and Day 1 and a urine pregnancy test on Days 10 and 14; positive urine pregnancy test will be confirmed with a serum pregnancy test. CD4 T cell count will be performed at Screening and Days 1 (baseline), 10, 14, and 15. A plasma sample for phenotypic and genotypic testing of HIV-1 resistance will be collected at Screening and Days 1, 10, 14, and 15. A whole blood sample for genotypic testing of HIV-1 resistance will be collected at Day 1. A complete physical examination will be performed at Screening and Days 1 (baseline), and 14. Symptom driven physical exam will be performed on Days 2 and 7. ECGs will be performed at Screening, Day 1 and Day 15.

On Day 14, all subjects will participate in a PK evaluation.

Samples for HIV-1 RNA will be collected at Screening and Days 1 (baseline), 3, 7, 10, 14, and 15.

Assessments of AEs and concomitant medications will be performed at each visit.

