7.2.2. Assessment of Severity

AE severity should be recorded and graded according to the GSI Grading Scale for Severity of Adverse Events and Laboratory Abnormalities ([Appendix 5](#)). For adverse events associated with laboratory abnormalities, the event should be graded on the basis of the clinical severity in the context of the underlying conditions; this may or may not be in agreement with the grading of the laboratory abnormality.

The distinction between the seriousness and the severity of an adverse event should be noted. Severe is a measure of intensity; thus, a severe reaction is not necessarily a serious reaction. For example, a headache may be severe in intensity, but would not be classified as serious unless it met one of the criteria for serious events.

7.3. Investigator Requirements and Instructions for Reporting Adverse Events and Serious Adverse Events to Gilead

Requirements for Collection Prior to Study Drug Initiation:

After informed consent, but prior to initiation of study medication, the following types of events should be reported on the eCRF: all SAEs and AEs related to protocol-mandated procedures.

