7.3.1. Adverse Events

Following initiation of study medication, all AEs, regardless of cause or relationship, until 30-days after last administration of study IMP must be reported to the eCRF database as instructed.

All AEs should be followed up until resolution or until the AE is stable, if possible. Gilead may request that certain AEs be followed beyond the protocol defined follow up period.

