7.3.2. Serious Adverse Events

All SAEs, regardless of cause or relationship, that occur after the subject first consents to participate in the study (i.e., signing the informed consent) and throughout the duration of the study, including the protocol-required post treatment follow-up period, must be reported to the eCRF database and Gilead PVE as instructed. This also includes any SAEs resulting from protocol-associated procedures performed after informed consent is signed.

Any SAEs and deaths that occur after the post treatment follow-up visit but within 30 days of the last dose of study IMP, regardless of causality, should also be reported. Investigators are not obligated to actively seek SAEs after the protocol-defined follow up period; however, if the investigator learns of any SAEs that occur after study participation has concluded and the event is deemed relevant to the use of IMP, he/she should promptly document and report the event to Gilead PVE

- All AEs and SAEs will be recorded in the eCRF database within the timelines outlined in the eCRF completion guideline.

Electronic Serious Adverse Event (eSAE) Reporting Process

- Site personnel record all SAE data in the eCRF database and from there transmit the SAE information to Gilead PVE within 24 hours of the investigator's knowledge of the event. Detailed instructions can be found in the eCRF completion guidelines.
- If for any reason it is not possible to record the SAE information electronically, i.e., the eCRF database is not functioning, record the SAE on the paper serious adverse event reporting form and submit within 24 hours to:

Gilead PVE contact information:

Fax: PPD

E-mail: PPD

- As soon as it is possible to do so, any SAE reported via paper must be transcribed into the eCRF Database according to instructions in the eCRF completion guidelines.
- If an SAE has been reported via a paper form because the eCRF database has been locked, no further action is necessary.
- For fatal or life-threatening events, copies of hospital case reports, autopsy reports, and other documents are also to be submitted by e-mail or fax when requested and applicable. Transmission of such documents should occur without personal subject identification, maintaining the traceability of a document to the subject identifiers.
- Additional information may be requested to ensure the timely completion of accurate safety reports.

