- v For female subject post-menopausal for less than two years, if FSH < 40 mIU/ mL a serum pregnancy test will be required

Appendix 3. Study Procedures Table – Sentinel Cohort 2/Randomized Cohort Part 1

		1	2	3	4	5	6	7	8	9	10	11	12	13	14	15
Informed Consent	X															
Medical History	X															
Concomitant Medication	X	X	X	X	X	X	X	X	X	X	X	X	X	X	X	X
Adverse Events	X	X	X	X	X	X	X	X	X	X	X	X	X	X	X	X
Complete Physical Exam	X	X														X
Symptom-Directed Physical Exam			X					X			X				X	
12-Lead ECG (performed supine)	X	X														X
Height	X															
Vital Signs and Weight	X	X		X				X			X				X	
Hematology Profile	X	X		X		X		X			X				X	X
Chemistry Profile	X	X		X		X		X			X				X	X
Urinalysis	X	X		X		X		X			X				X	X
Metabolic Profile ^k		X														
Estimated Glomerular Filtration Rate	X	X		X		X			X			X			X	
Serum Pregnancy Test ^l	X	X														
Urine Pregnancy Test ^l	X	X									X				X	
FSH Testing ^v	X															
Plasma, Serum, CCI Storage Sample		X		X		X		X			X	X			X	X
HCV Serology ^m	X															
HBV blood panel	X															
Plasma HIV-1 RNA	X	X		X				X			X				X	X
CD4+ Cell Count	X	X									X				X	X
HIV-1 Genotype/ Phenotype ^j	X	X									X					X
Whole blood sample for genotypic testing		X														

	1	2	3	4	5	6	7	8	9	10	11	12	13	14	15
CCI															
Intensive PK Sampling ^p														X	
PBMC Sampling ^f														X	
Randomization ^s	X														
Collect Subject Dosing Diary to Subjects															X
In-clinic Dosing ^t	X	X	X	X	X	X	X	X	X	X	X	X	X	X	X

[figure not shown]
Study Procedures	Part 2 Weeks ^{e,j} (+/- 4 days)								CCI		30 Day Follow-up ^f	ESDD ^h
	Day1	1	2	4	8	12	18	24	Every 12 Weeks			
Concomitant Medication	X	X	X	X	X	X	X	X	X		X	X
Adverse Events	X	X	X	X	X	X	X	X	X		X ⁱ	X
Complete Physical Exam	X					X		X				X
Symptom-Directed Physical Exam		X	X	X	X		X		X		X ⁱ	
12-Lead ECG (performed supine)	X							X			X	
Vital Signs and Weight	X	X	X	X	X	X	X	X	X		X	X
Hematology Profile	X	X	X	X	X	X	X	X	X		X ⁱ	X
Chemistry Profile	X	X	X	X	X	X	X	X	X		X ⁱ	X
Urinalysis	X			X		X		X	X		X ⁱ	X
Metabolic Profile ^k	X					X ^k		X ^k	X			
Estimated Glomerular Filtration Rate	X	X	X	X	X	X	X	X	X		X ⁱ	X
Serum Pregnancy Test ^l												
Urine Pregnancy Test ^l	X			X	X	X	X	X	X		X	X
Plasma, Serum, CCI Storage Sample	X			X	X	X	X	X	X		X	X
HCV Serology ^m								X				

Study Procedures	Part 2 Weeks ^{e,j} (+/- 4 days)								CCI	30 Day Follow-up ^f	ESDD ^h
	Day1	1	2	4	8	12	18	24	Every 12 Weeks		

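### The AE-recording bullet in five post-dose visit lists carries the pre-dose scope and conflicts with Section 7.3.1, so non-serious treatment-emergent AEs could be left out

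*Protocol*

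**What the plan says.** Protocol Section 6.3.1 lists the Part 1 visit procedures. Its AE line reads: "Record any SAEs and all AEs related to protocol mandated procedures occurring after signing of the consent form". The same line stands in Section 6.3.2 (Part 2 Day 1), Section 6.3.3 (Part 2 Weeks 1-24), Section 6.4.1 (early study drug discontinuation visit) and Section 6.4.2 (30-day follow-up visit).

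Two other places tie that scope to the time before dosing. Section 6.2.1 opens its rule with "From the time of obtaining informed consent through the first administration of IMP, all serious adverse events (SAEs), as well as any AEs" and goes on to limit those AEs to ones related to protocol procedures. Section 7.3, under its heading for the time before study drug starts, says that "the following types of events should be reported on the eCRF: all SAEs and AEs related to protocol-mandated procedures".

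For the time after first dose, Section 7.3.1 says: "Following initiation of study medication, all AEs, regardless of cause or relationship, until 30-days after last administration of study IMP must be reported".

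Other text agrees with Section 7.3.1. Section 7.3.2 states: "All AEs and SAEs will be recorded in the eCRF database within the timelines outlined in the eCRF completion guideline". The synopsis states for Part 1: "Assessments of AEs and concomitant medications will be performed at each visit". The Appendix 3 procedures table has a row headed simply "Adverse Events", marked at every visit. Section 9.1.5 asks for all AEs in the source record.

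**The concern.** The pre-dose rule appears to have been carried forward into lists that apply after dosing. Section 6 is what a site works through at a visit, and there the collection rule is narrower than the one in the reporting section.

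The events that fall between the two rules are AEs after first dose that are neither serious nor caused by a study procedure. That group includes ordinary drug-related AEs. It also includes non-serious Grade 3 or 4 events judged possibly related to study drug, which the sentinel cohort stopping rule in Section 6.5.1 counts whether or not they are serious. The setting makes completeness matter: Section 1.8.1 says that no clinical safety data were available for the 180 mg dose given in Sentinel Cohort 2.

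**Working it through.** No arithmetic underlies the main point. The check sets the places side by side.

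| Place in protocol | Period covered | AE scope |
|---|---|---|
| 6.2.1 and 7.3 | Consent to first dose | SAEs and procedure-related AEs |
| 6.3.1 | Part 1: Screening, Day 1, dosing days | Same narrow scope |
| 6.3.2 | Part 2 Day 1 | Same narrow scope |
| 6.3.3 | Part 2 Weeks 1-24 | Same narrow scope |
| 6.4.1 | Early discontinuation visit | Same narrow scope |
| 6.4.2 | 30-day follow-up visit | Same narrow scope |
| 7.3.1 | First dose to 30 days after last dose | All AEs |
| 7.3.2, 9.1.5, synopsis, Appendix 3 row | Study visits and records | No restriction by type |

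1. *Does each list reach past first dose?* Yes. The 6.3.1 list mixes Screening with dosing days. Its examination, vital-sign and ECG bullets name their days; the AE bullet names none, so it covers them all. The other four lists concern subjects who have already had study drug or placebo in Part 1. At Part 2 Day 1 the gap since Part 1 dosing is limited by Section 6.3.2 to 14 days (Sentinel Cohort 1) or 9 days (the other cohorts). Both are inside the 30 days of Section 7.3.1, so the all-AE rule is already in force.

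2. *Does any list state the wider rule elsewhere?* No. Count: 5 of 5 lists carry the narrow scope and 0 of 5 state the wide one. For the three on-treatment lists (6.3.1, 6.3.2, 6.3.3) it is 3 of 3.

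3. *Does the procedures table settle it?* Not by itself. Section 6 opens by saying that the procedures are tabulated in the appendices and described in the text, and the text describing the AE row is the narrow bullet. The sentence in Section 7.6 that the more conservative criteria prevail concerns toxicity management, not AE collection.

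4. *Where would omitted events be used?* Protocol Section 8.6.2 and SAP Section 7.1.5.1 both define a treatment-emergent AE as any AE with onset on or after the start of study drug, and SAP Section 7.1.6 builds its tables on that. The SAP applies the definition to Part 1 only and lists Part 2 AEs. As worded in Section 6.5.1, the sentinel rule concerns dosing during Part 1. So the 6.3.1 list matters most for the tables and the stopping rule, while Part 2 AEs feed listings.

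5. *How far past last dose can these visits fall?* The discontinuation visit may be 72 hours (3 days) after stopping; follow-up for those who leave is 30 days after that visit, with a window of 6 days: 3 + 30 + 6 = 39 days. For those who complete treatment it is 30 + 6 = 36 days. Both can exceed the 30 days of Section 7.3.1. Subjects who stop drug are also asked to keep attending through Week 24. Replacement wording therefore needs a time limit.

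**The case against.** The strongest reply is that full collection is already mandatory. Section 7.3 is the investigators' reporting section, it separates the periods before and after first dose, and 7.3.1 is phrased as an obligation. Section 6.2.1 sends readers to Section 7. Sections 7.3.2 and 9.1.5, the synopsis and the Appendix 3 row agree. This stands, and it settles what was intended. It does not make the five bullets correct.

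A reader might infer that sites are told to record only these events. No bullet contains that word; the restriction arises because it is the sole AE-recording instruction in each list. A reader might also infer that non-serious AEs would be lost. Given the binding text elsewhere, loss is a risk at a site that relies on the Section 6 lists, not an expected result.

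On the stopping rules, Section 7.6.3 separately requires treatment-emergent toxicities to be brought to the sponsor's Medical Monitor, the by-subject rule turns on the investigator's own judgement, and the laboratory limb uses laboratory results. This lowers the risk. That one missing event could decide a two-subject rule is true of any such threshold and does not measure this defect.

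Nor can it be said that every post-dose contact is affected. The contents list shows a redacted entry after 6.3.3, the available 6.3.3 list is short, and the 6.3.1 list includes Screening, where the narrow scope is right.

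**Conclusion.** The contradiction is real: in all five available lists, an operative collection instruction is wrong as written for the time after first dose. It should be corrected because it bears on the treatment-emergent AE tables and on the Grade 3 or 4 limb of the sentinel stopping rule.

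The size is five bullets. The number of AEs at stake cannot be estimated, since it depends on how sites read the protocol and on eCRF completion guidelines that are not among the documents. The documents support a risk of under-recording; they do not show that any event was missed, or that a stopping decision was affected.

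The conclusion assumes that the redacted text holds no wider AE instruction for these same visits. SAP Section 2.4 reports that the study was discontinued, which limits what an amendment could still change.

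**What to change.** In Sections 6.3.1 (from first dose), 6.3.2, 6.3.3, 6.4.1 and 6.4.2, replace the bullet with wording such as: *Record all AEs and SAEs, whatever their cause or relationship to study drug, for the collection periods defined in Section 7.3.1 (AEs: to 30 days after last IMP) and Section 7.3.2 (SAEs).* Keep the narrow wording only for the period from consent to first dose, including the Screening part of the 6.3.1 list.

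The cost is the wording of five bullets. With the 30-day limit stated, it adds no data collection beyond what Sections 7.3.1 and 7.3.2 already require. For data already collected, comparing the source records that Section 9.1.5 requires with the eCRF would show whether any AEs were left out before the tables are relied on. That comparison costs monitoring time, limited to the subjects enrolled.
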